### 3 OBJECTIVES AND ENDPOINTS

#### 3.1 Objectives

##### Primary Objectives:

- To assess the safety and tolerability profile of OsrHSA when IV administered as single dose

##### Secondary Objectives:

- To characterize the PK of OsrHSA when IV administered as single dose
- Immunogenicity profiles of OsrHSA when IV administered as single dose

##### Exploratory Objectives:

- To assess changes in serum albumin level, colloid osmotic pressure, blood pressure and body weight when IV administered as single dose

#### 3.2 Endpoints

##### Primary Endpoints

- 1) Safety and tolerability profile including adverse events, changes in safety assessment parameters (e.g. vitals, ECGs, clinical laboratory results)

##### Secondary Endpoints

- 1) PK parameters:  $AUC_{0-\infty}$  and  $AUC_{0-t}$ ,  $C_{max}$ ,  $t_{1/2}$ ,  $CL$ ,  $V_{ss}$ , etc.
- 2) ADA: Samples confirmed to be positive for ADA will be further tested for NAb.

##### Exploratory Endpoints

- Changes in serum albumin level and colloid osmotic pressure
- Changes in body weight and blood pressure

## 4 STUDY DESIGN

### 4.1 Overall Study Design

This is a Phase 1 randomized, double blinded, placebo-controlled, single dose escalation study in healthy volunteers to evaluate safety, tolerability, PK, PD and immunogenicity of OsrHSA (See [study design schema](#)).

### 4.2 Study Process

The trial will include a screening period, treatment period, and follow-up period of 30 days after administration. The screening period will be up to 28 days prior to investigational product administration. The screening process will initiate upon completion of the informed consent process. Once consent is provided by each participant, a thorough screening process will take place, including detailed medical history, physical examination, vital signs, concomitant medications, safety labs (see Table 1), 12 lead electrocardiogram, urine pregnancy test, urinalysis, serology panel (refer Table 1), assessment of inclusion and exclusion criteria. Upon completion of the screening, qualified subjects will be randomized to OsrHSA or placebo (6:2). Each enrolled subject will receive one single assigned dose of OsrHSA or placebo. The investigator and subjects will be blinded to treatment assignment. During the study, subjects will be evaluated for safety and toxicity, PK/PD, and activity of OsrHSA.

OsrHSA or placebo will be administered as single IV infusion at a rate lower than 2 ml/ min to the subjects. The actual start and stop times of the infusions, along with any interruptions in the infusion will be recorded. Subjects will have end-of-study (EOS) follow-up visits on Day 30 after infusion.

The planned doses are 20, 40, 80, 140, and 200 mg/kg (Table 2), dose level(s) higher than 200 mg/kg might be an option(s) based on emerging data from this study and ongoing China clinical trial, if that is the case, an amendment will be submitted.

The protocol for the repeat dose study will be submitted as an amendment to the IND after the single dose study has been completed and analyzed. The dose schedule of the repeat dose study will be based on results obtained from the single dose study. The safety of the dose that will be used in the repeat dose study will be established before the initiation of the repeat dose study.

Dose escalation will occur sequentially after review of safety data for each dosing cohort by the safety review committee (SRC). Dose escalation to the next dose level will proceed uninterrupted as long as no pre-defined DLT or stopping criteria are met.

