#### 4.2.1 Definition of Dose Limiting Toxicity (DLT):

AEs will be graded according to the FDA Guidance for Industry *Toxicity Grading Scale for Healthy Adult and Adolescent Volunteers Enrolled in Preventive Vaccine Clinical Trials*. DLT is

defined according to the criteria below as any TEAEs occurring during the DLT observation period (7 days) and considered to be related to OsrHSA:

*Any Grade  $\geq$  3 AE or laboratory abnormality as defined in the FDA Guidance for Industry Toxicity Grading Scale for Healthy Adult and Adolescent Volunteers Enrolled in Preventive Vaccine Clinical Trials*

All Grade 3 toxicities for vital signs and laboratory parameters must be confirmed with a repeat measurement obtained within 1 hour or as soon as possible for vital signs and within 24 hours for laboratory parameters.

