#### **4.2.2 Dose-escalation Criteria:**

Tolerability and safety of subjects in a cohort will be reviewed by the SRC which is comprised of an independent Medical Monitor, site Principal Investigator, and Sponsor Study Director. Dose escalation may be stopped at any time based upon the Sponsor or Investigator's clinical assessment or judgment. Upon completion of the DLT observational period (first week after dosing), the SRC will examine safety data through Week 1 for each dose cohort in combination with all available, previously accumulated safety data, as well as available PK data, if any, from all subjects enrolled in the study to date. All cohorts will enroll 8 subjects (safety data from at least 6 or 7 subjects would be needed for SRC meeting, in case a subject discontinues the study), if no more than 2 out of 8 subjects experiences DLT as defined in the section 4.2.1, dose will be escalated to the next dose level.

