#### **4.2.3 Subject Stopping Criteria:**

Dosing will be permanently stopped for any individual subject experiencing any of the following:

- Any SAE, regardless of causality to the study drug.

- Subject experience DLT.
- Hypersensitivity or anaphylactic reaction following start of infusion.
- Medical condition that is judged by the Investigator as to jeopardize the subject's safety if he or she continues to receive the study drug.
- QTc prolongation defined as QTcF increasing  $\geq 60$  msec and persisting for at least 10 minutes or QTcF  $> 500$  msec and persisting for at least 30 minutes, or episode of torsade de pointes.

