#### 4.2.4 Dose Escalation Stopping Criteria:

Dose escalation will not occur if any of the following criteria are met:

- Subject stopping rules met for  $\geq 2$  subjects in the same cohort suggesting to the Investigator that other subjects in the cohort are at risk for similar adverse drug reactions.
- Any SAE as defined in the section 10.1 in any participant receiving study drug unless obviously not related.
- $\geq 2$  out of 8 subjects experience toxicity  $\geq$  Grade 3 as defined in the Food and Drug Administration (FDA) Guidance for Industry *Toxicity Grading Scale for Healthy Adult and Adolescent Volunteers Enrolled in Preventive Vaccine Clinical Trials*.

The safety review will initially be performed on blinded data, and if any of the above criteria are met, the cohort will be subsequently unblinded to all SRC members and the safety and tolerability reassessed. Upon unblinding, the dose may be determined to be safe and tolerable, on the basis of events observed in the OsrHSA vs. placebo groups, allowing for dose escalation to proceed.

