### **10.9 Safety Review Committee (SRC)**

To ensure the safety of study subjects and integrity of the study data, a Safety Review Committee (SRC) consisting of the study Investigators, Study Director, designated Medical Monitor and/or other key study personnel will convene to review cumulative data for the study. SRC will conduct dose decision teleconference meeting before each dose escalation.

Before each dose escalation, the Investigators, Study Director and Medical Monitor(s), together, will review the safety data from the current cohort after enough subjects (7-8) have completed the first week. It will be determined whether escalation to the next dose level can proceed or whether dose level should be de-escalated.

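### The dose-escalation rule is worded inconsistently: section 4.2 gives no DLT count and is out of line with 4.2.2 and 4.2.4 at one DLT, and 4.2.2 and 4.2.4 contradict each other at exactly two of eight

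*Combined protocol and SAP*

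**What the plan says.** Four parts of section 4.2 bear on whether the next cohort opens.

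- **4.2 Study Process**, after requiring SRC review of each cohort: "Dose escalation to the next dose level will proceed uninterrupted as long as no pre-defined DLT or stopping criteria are met". There is no number of subjects, no cross-reference, and no statement of what happens otherwise.
- **4.2.1** defines a DLT by subject-level events of Grade 3 or higher, covering "any TEAEs occurring during the DLT observation period (7 days) and considered to be related to OsrHSA".
- **4.2.2** sets a cohort threshold: "if no more than 2 out of 8 subjects experiences DLT as defined in the section 4.2.1, dose will be escalated".
- **4.2.3** lists the criteria that end dosing for an individual. One of them is "Subject experience DLT".
- **4.2.4** rules escalation out in three cases. The first is when the subject stopping rules are met for 2 or more "subjects in the same cohort suggesting to the Investigator that other subjects in the cohort are at risk for similar adverse drug reactions". The second is "Any SAE as defined in the section 10.1 in any participant receiving study drug unless obviously not related". The third is when at least 2 "out of 8 subjects experience toxicity" of Grade 3 or higher. If any of these is met, the cohort is unblinded to the SRC, which may then find the dose tolerable and allow escalation.

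Section 10.9 adds a general SRC decision before each step: "It will be determined whether escalation to the next dose level can proceed or whether dose level should be de-escalated".

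**The concern.** These are the rules under which healthy volunteers are exposed to a higher dose, so the action at each event count should be readable from one place. It is not.

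After one DLT, section 4.2 taken at its word no longer offers uninterrupted escalation. It does not say what an interruption consists of, who lifts it, or on what data. Section 4.2.2 meanwhile says that the dose goes up. The unblinded reassessment in 4.2.4 does not fill the gap, because it starts only when a 4.2.4 criterion is met, and one non-serious DLT meets none.

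After two DLTs the problem is sharper, because one section escalates and another rules escalation out. Repairing only that conflict would leave the sentence in 4.2 as it is.

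**Working it through.** **Inputs.** Each cohort has 8 subjects, 6 on OsrHSA and 2 on placebo (Table 2), and five cohorts are planned. The plan states no DLT rate and no escalation probability, and section 11.2 says that the sample size was not set on statistical grounds. There is therefore no figure of the plan's own to reproduce, and every DLT rate p below is an assumption.

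**Step 1: the sections side by side.**

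| Cohort outcome | 4.2, read literally | 4.2.2 | 4.2.4 |
|---|---|---|---|
| No DLT and no other stopping event | Uninterrupted | Escalate | Not triggered |
| One non-serious DLT | Condition fails; next step unstated | Escalate | Not triggered |
| One DLT that is also an SAE, subject on study drug | Condition fails | Escalate (no SAE exception in the count) | Ruled out, subject to unblinded reassessment |
| One DLT plus an unrelated Grade 3 or higher event in another subject | Condition fails | Escalate (one DLT) | Ruled out, subject to reassessment: the count states no relatedness or 7-day limit |
| Two DLTs | Condition fails | Escalate | Ruled out, subject to reassessment |
| Three or more DLTs | Condition fails | Threshold exceeded; action not stated | Ruled out, subject to reassessment |

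Every DLT is by definition of Grade 3 or higher, so two DLTs always meet the third criterion of 4.2.4. The conflict in the two-DLT row therefore does not depend on interpretation. The one-DLT row depends on reading the DLT criteria in 4.2 as the subject-level ones in 4.2.1 and 4.2.3.

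**Step 2: how often each count would arise.** Suppose only the 6 active subjects are at risk, independently and at the same rate p. Then P(exactly 1) = 6p(1−p)^5 and P(exactly 2) = 15p²(1−p)^4.

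| Assumed p | Exactly one | Exactly two |
|---|---|---|
| 0.05 | 6 × 0.05 × 0.95^5 = 0.232 | 15 × 0.05² × 0.95^4 = 0.031 |
| 0.10 | 6 × 0.10 × 0.90^5 = 0.354 | 15 × 0.10² × 0.90^4 = 0.098 |
| 0.15 | 6 × 0.15 × 0.85^5 = 0.399 | 15 × 0.15² × 0.85^4 = 0.176 |
| 0.20 | 6 × 0.20 × 0.80^5 = 0.393 | 15 × 0.20² × 0.80^4 = 0.246 |
| 0.30 | 6 × 0.30 × 0.70^5 = 0.303 | 15 × 0.30² × 0.70^4 = 0.324 |

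Sections 4.2.2 and 4.2.4 count out of 8, and the first review is blinded. With all 8 subjects at the same rate, exactly one against exactly two is 0.279 against 0.051 at 5%, 0.383 against 0.149 at 10%, 0.336 against 0.294 at 20%, and 0.267 against 0.311 at 25%.

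**Step 3: when one is likelier than two.** Setting np(1−p)^(n−1) > [n(n−1)/2]p²(1−p)^(n−2) gives p < 2/(n+1). That is 2/7 = 0.286 for n = 6 and 2/9 = 0.222 for n = 8.

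**Step 4: low rates across the study.** If all five cohorts run at one constant rate among 6 active subjects, the chance that at least one cohort has exactly one DLT is 1 − (1 − P(exactly 1))^5. At p = 0.01 this is 1 − (1 − 0.0571)^5 = 0.255. At p = 0.02 it is 1 − (1 − 0.1085)^5 = 0.437.

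**The case against.** The strongest reply is that nothing conflicts at one DLT. The sentence in 4.2 closes an introductory text and stands just before 4.2.1 to 4.2.4, so its DLT and stopping criteria can be read as a pointer to the cohort counts that follow. Section 4.2.3 shows what the protocol attaches to one subject's DLT: dosing ends for that subject, not for the cohort. The sections that set the escalation criteria both allow escalation after one non-serious DLT. The SRC reviews every cohort, and 4.2.2 lets the sponsor or investigator stop escalation at any time, so no such cohort passes unreviewed.

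Most of this stands. A reader might infer that 4.2 and 4.2.2 lay down opposite rules for one DLT. The documents do not support that. Section 4.2 says when escalation runs without interruption and does not prohibit it otherwise, so a pause for SRC review followed by escalation would satisfy both sections. A reader might also infer that one DLT is simply the commonest non-zero result. That holds only below the assumed rates in step 3, and the documents give no rate.

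Two things remain. Section 4.2 carries neither a count nor a cross-reference, so the benign reading has to be supplied by the reader. If it is supplied, the sentence then points to two sections that contradict each other at exactly 2 of 8. The reassessment in 4.2.4 softens that contradiction without removing it, because 4.2.2 escalates at two DLTs without requiring that step.

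**Conclusion.** This is an internal inconsistency in a safety decision rule, of two strengths. At one non-serious DLT, 4.2.2 and 4.2.4 agree and 4.2 is the loosely worded outlier. The instructions are incomplete rather than opposed, and this part alone is a clarification of lower priority. At exactly 2 of 8, 4.2.2 and 4.2.4 contradict each other directly. They also part company after a single DLT when that DLT is an SAE in a subject on study drug, or when another subject has an unrelated event of Grade 3 or higher.

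The one-DLT case is not remote: about 23% to 40% per cohort over assumed rates of 5% to 20% among 6 active subjects. These figures rest on independent subjects, a common rate and no placebo DLTs. They show how often the wording would be put to use. They are not evidence of the inconsistency, which rests on the text alone.

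**What to change.** Reconcile 4.2, 4.2.2, 4.2.3 and 4.2.4 in one table that gives the action for 0, 1, 2 and 3 or more DLTs per cohort. Add rows for a DLT that is also an SAE, and for one DLT together with an unrelated Grade 3 or higher event in another subject. State whether the Grade 3 count in 4.2.4 is limited to related events and to the 7-day window. Where the action is a pause, state who reviews, on which data (blinded or unblinded), and who releases it. Reword the sentence in 4.2 so that it refers to the table and sets no condition of its own.

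The action at each count is for the sponsor and the SRC to decide; none is proposed here. The cost is a short text clarification in a protocol amendment, with no added subjects, visits or analyses. The one-DLT wording and the 2-of-8 conflict should be settled in the same edit.

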#### 4.2.1 Definition of Dose Limiting Toxicity (DLT):

AEs will be graded according to the FDA Guidance for Industry *Toxicity Grading Scale for Healthy Adult and Adolescent Volunteers Enrolled in Preventive Vaccine Clinical Trials*. DLT is

defined according to the criteria below as any TEAEs occurring during the DLT observation period (7 days) and considered to be related to OsrHSA:

*Any Grade  $\geq$  3 AE or laboratory abnormality as defined in the FDA Guidance for Industry Toxicity Grading Scale for Healthy Adult and Adolescent Volunteers Enrolled in Preventive Vaccine Clinical Trials*

All Grade 3 toxicities for vital signs and laboratory parameters must be confirmed with a repeat measurement obtained within 1 hour or as soon as possible for vital signs and within 24 hours for laboratory parameters.

**Table 2 Dose Escalation Schedule**

Dose Escalation Level	Dose (mg/kg)	Subjects (OsrHSA:placebo)
cohort 1	20, IV	8(6:2)
cohort 2	40, IV	8(6:2)
cohort 3	80, IV	8(6:2)
cohort 4	140, IV	8(6:2)
cohort 5	200, IV	8(6:2)

#### **4.2.2 Dose-escalation Criteria:**

Tolerability and safety of subjects in a cohort will be reviewed by the SRC which is comprised of an independent Medical Monitor, site Principal Investigator, and Sponsor Study Director. Dose escalation may be stopped at any time based upon the Sponsor or Investigator's clinical assessment or judgment. Upon completion of the DLT observational period (first week after dosing), the SRC will examine safety data through Week 1 for each dose cohort in combination with all available, previously accumulated safety data, as well as available PK data, if any, from all subjects enrolled in the study to date. All cohorts will enroll 8 subjects (safety data from at least 6 or 7 subjects would be needed for SRC meeting, in case a subject discontinues the study), if no more than 2 out of 8 subjects experiences DLT as defined in the section 4.2.1, dose will be escalated to the next dose level.

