## **5 PATIENT POPULATION**

### **5.1 Number of Subjects and Description of Population**

This study will enroll up to 40 healthy male or female subjects, 8 subjects for each of 5 cohorts, 18-55 years old, or more subjects might be recruited based on emerging data from this study and ongoing China clinical trial. Subject Selection and Numbering:

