## **5.8 Randomization and blinding**

Subjects in the clinical site will be 6:2 randomized to receive either the study product or placebo prior to dosing, the randomization code will not be available to the Bioanalytical Division until the clinical and analytical phases have been completed for each cohort.

Both the principal investigator and subjects will be blinded as to whether a subject is receiving study product, or placebo. A designated person in the Investigational Pharmacy will dispense the appropriate drug accordingly. The Safety Review Committee can request unblinded randomization scheme in order to evaluate the data.

Each bottle administered to subjects will have a unique code, and quick unblinding will be performed by Investigational Drug Pharmacy, the principal investigator, or the sponsor, should a medical emergency arise for a participant.

Upon completion of the study participation, all subjects will be unblinded

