### **11.2 Determination of Sample Size**

An estimated total of 40 subjects will enroll in this study. The sample size for this study was determined based on clinical, rather than statistical considerations. A projected sample size of 8 subjects per dosing cohort is considered to be of reasonable size to achieve the objectives of this single dose escalation trial. Other factors may contribute to the final sample size, which is dependent upon the observed safety and tolerability profile, and determines the number of subjects per dose cohort, number of replacements, as well as the number of dose escalations required to achieve the maximal proposed dose of the study drug.

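### The minimum data for an SRC escalation review is counted over both arms, so a dose can be cleared with complete Week 1 data from only 4 subjects on OsrHSA (5 under section 10.9)

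*Combined protocol and SAP*

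**What the plan says.** **Allocation.** Table 2 gives every cohort 8 subjects, 6 on OsrHSA and 2 on placebo (saline). Section 5.1 plans "8 subjects for each of 5 cohorts", and section 5.8 states: "Subjects in the clinical site will be 6:2 randomized to receive either the study product or placebo prior to dosing".

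**Sample size.** Section 11.2: "An estimated total of 40 subjects will enroll in this study". It adds: "The sample size for this study was determined based on clinical, rather than statistical considerations". No target DLT rate or error rate is given.

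**Minimum for a review.** Section 4.2.2: "safety data from at least 6 or 7 subjects would be needed for SRC meeting, in case a subject discontinues the study". Section 10.9 sets the figure at 7 to 8 with the first week completed. Neither mentions treatment arm.

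**Escalation limits.** Section 4.2.2 escalates "if no more than 2 out of 8 subjects experiences DLT as defined in the section 4.2.1". Section 4.2.4, third criterion, blocks escalation when 2 or more of 8 have toxicity of Grade 3 or higher. Section 4.2.1 defines a DLT as a drug-related event or laboratory abnormality of Grade 3 or higher within 7 days.

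**Blinding.** Section 4.2.4: "The safety review will initially be performed on blinded data". If a criterion is met, the SRC is unblinded to the cohort and compares events by arm, after which escalation may still go ahead. Section 5.8 also lets the SRC ask for the codes, and says of the pharmacy: "A designated person in the Investigational Pharmacy will dispense the appropriate drug accordingly".

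**The concern.** Only subjects given a dose can show whether it is toxic. A minimum counted over both arms does not fix how many such subjects stand behind a decision to go higher, and on blinded data the committee cannot tell.

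Early loss is foreseeable. Section 4.2.2 sets its minimum with discontinuation in mind. Table 1 tests alcohol and cotinine on Days 3, 5 and 8, section 6.4.1 lists a positive result as a reason for removal, and section 6.4 withdraws non-compliant subjects. Section 6.4.2 ends data collection once a subject is off study. Replacement under 6.4.3 is optional, so it does not guarantee 6 exposed subjects.

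The stake is a step to a higher dose in healthy volunteers on less information than the review figure suggests, in a study whose primary objective is safety and tolerability.

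**Working it through.** **1. The plan's own figure.** 5 cohorts x 8 = 40, as section 11.2 says; that is 5 x 6 = 30 on OsrHSA and 5 x 2 = 10 on saline.

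**2. Who is among the reviewed subjects.** Assume losses are unrelated to arm. With m of 8 evaluable, P(a on OsrHSA) = C(6,a) x C(2,m-a) / C(8,m).

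- m = 8: a = 6 with certainty.
- m = 7: a = 5, 6/8 = 75%; a = 6, 2/8 = 25%.
- m = 6: a = 4, 15/28 = 53.6%; a = 5, 12/28 = 42.9%; a = 6, 1/28 = 3.6%.

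The floor is therefore 4 if 6 subjects suffice, and 5 under the 7 in section 4.2.2 or under section 10.9. At six evaluable, 4 exposed is the most likely split.

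**3. What a clean review shows.** With no DLT in n exposed subjects, the one-sided 95% upper limit is 1 - 0.05^(1/n):

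- n = 4: 52.7%
- n = 5: 45.1%
- n = 6: 39.3%

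**4. What passes without unblinding.** Every DLT is Grade 3 or higher (4.2.1), so two DLTs always meet the third criterion of 4.2.4. The most that avoids that trigger is one subject with a Grade 3 or higher event. If that subject is on OsrHSA, the rate among those exposed is 1/6 = 17%, 1/5 = 20% or 1/4 = 25%.

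The documents give no DLT rate. Assume a rate p per OsrHSA subject, none on saline, and no other 4.2.4 criterion met. Then P(one or fewer) = (1-p)^n + n p (1-p)^(n-1). At p = 0.3:

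- n = 4: 0.2401 + 0.4116 = 0.65
- n = 5: 0.1681 + 0.3602 = 0.53
- n = 6: 0.1176 + 0.3025 = 0.42

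Over a range of assumed rates:

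| True DLT rate | 4 exposed | 5 exposed | 6 exposed |
|---|---|---|---|
| 0.2 | 0.82 | 0.74 | 0.66 |
| 0.3 | 0.65 | 0.53 | 0.42 |
| 0.5 | 0.31 | 0.19 | 0.11 |

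**5. The 2-of-8 limit per treated subject.** Nominally 2/8 = 25%. In a full cohort with both DLTs on OsrHSA it is 2/6 = 33%.

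**6. Passages that conflict.** On two DLTs, section 4.2.2 lets escalation proceed and section 4.2.4 blocks it pending unblinded review. On the minimum, section 4.2.2 says 6 or 7 and section 10.9 says 7 to 8. Neither limit says what replaces the 8 when fewer are evaluable.

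**The case against.** The strongest reply is that section 4.2.4 already separates the arms when it matters: two Grade 3 or higher events unblind the cohort, and the SRC may request the codes at any time. This stands in part. A reader might infer that two DLTs can pass on the pooled count, and that a 50% DLT rate among those treated is tolerated. The documents do not support that. Two DLTs always trigger arm-level review, and 2/4 = 50% needs six evaluable subjects, both absent subjects on OsrHSA and both DLTs on OsrHSA. Likewise, section 4.2.2 read alone would be met 69% of the time with 4 exposed at a true 50% rate; with the 4.2.4 trigger applied, the figure is 31%.

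What the reply leaves open is the quiet cohort. With no event or one, and no other criterion met, nothing prompts unblinding. Requesting codes is optional, and the site principal investigator sits on the SRC but is meant to stay blinded. After unblinding, no limit per exposed subject is stated.

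A second reply is that a dosed subject who leaves was still exposed. That is right: section 7.1 records all AEs from the start of dosing, section 11.3.2 counts everyone treated, and a drug-related departure may itself have been recorded as toxicity. It would be wrong to infer that only four people received the dose; the claim concerns complete Week 1 data. The documents do not say whether an early leaver counts as evaluable for DLT.

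Third, losing two of eight within a week of a single dose may be uncommon. The documents give no loss rate, so the 54% is conditional on that loss. The SRC also knows the 6:2 design, and so knows the range, though not which value applies.

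**Conclusion.** The point holds as a gap in the review minimum. No section sets the number of OsrHSA-treated subjects needed, so a dose can be cleared on complete Week 1 data from 4 exposed subjects under the lower figure in 4.2.2, or 5 under 10.9. Compared with a full 6, the upper limit after a clean review rises from 39% to 53% (45% with 5). At an assumed 30% DLT rate, the chance of one or fewer events rises from 42% to 65% (53% with 5).

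These sizes rest on losses independent of arm, no DLTs on saline, and counting only subjects with a completed first week. The finding does not show that the plan treats saline recipients as exposed once events accumulate. It is worth correcting because the remedy is cheap and the study is a safety study.

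**What to change.** - In sections 4.2.2 and 10.9, state the SRC minimum as a number of OsrHSA-treated subjects with completed Week 1 data. The sponsor sets the number.
- Have the dispensing pharmacist confirm yes or no that it is reached, without listing allocations.
- State whether a dosed subject who leaves before Day 8 counts as evaluable for DLT.
- Report DLT rates per OsrHSA-treated subject.
- Reconcile 4.2.2 with 4.2.4 on two DLTs and on the denominator when fewer than 8 are evaluable, and 4.2.2 with 10.9 on 6 or 7 against 7 to 8. Which rule is right is for the sponsor and investigators, not this review.

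**Cost.** Protocol wording and one confirmation per cohort. A review may occasionally wait for one more subject. The answer also gives slight information on the allocation mix: because 6:2 is fixed, it can at worst point to the arm of an absent subject. For example, with 7 evaluable, an answer on whether all 6 OsrHSA subjects are included would do so. The sponsor should weigh this when choosing the number.

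### At exactly 2 DLTs of 8, section 4.2.2 directs escalation while section 4.2.4 blocks it pending unblinding and SRC reassessment

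*Combined protocol and SAP*

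**What the plan says.** Section 4.2.1 defines a DLT as "defined according to the criteria below as any TEAEs occurring during the DLT observation period (7 days) and considered to be related to OsrHSA". The severity condition is any adverse event or laboratory abnormality of Grade 3 or higher on the FDA vaccine-trial toxicity scale.

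Section 4.2.2 has the SRC review first-week data for each cohort of 8 and then sets the go rule: "if no more than 2 out of 8 subjects experiences DLT as defined in the section 4.2.1, dose will be escalated". The rule does not mention section 4.2.4. The same section lets the Sponsor or Investigator stop escalation at any time.

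Section 4.2.3 lists "Subject experience DLT" among the reasons for stopping an individual subject.

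Section 4.2.4 opens with "Dose escalation will not occur if any of the following criteria are met" and gives three criteria:

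- the first, on individual stopping events, applies when the subject stopping rules are met for 2 or more "subjects in the same cohort suggesting to the Investigator that other subjects in the cohort are at risk for similar adverse drug reactions";
- the second, on serious adverse events, needs only one case: "Any SAE as defined in the section 10.1 in any participant receiving study drug unless obviously not related";
- the third, on the toxicity count, applies when 2 or more "out of 8 subjects experience toxicity" of Grade 3 or higher on the FDA scale.

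It continues: "The safety review will initially be performed on blinded data". If a criterion is met, the cohort is unblinded to all SRC members and reassessed. Escalation may then go ahead if the comparison of OsrHSA with placebo supports it.

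The last sentence of section 4.2 allows uninterrupted escalation provided that neither DLT nor stopping criteria have been met. Section 10.9 has the SRC decide before each escalation whether to proceed or de-escalate. Section 5.8 says the SRC may ask for the unblinded allocation.

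**The concern.** The two sections use the same count, 2 of 8, on opposite sides of the decision. Section 4.2.2 includes 2 among the counts that lead to escalation, and section 4.2.4 includes 2 among the counts that block it. The events counted are not different in kind, because a DLT is a Grade 3 or higher event that is also related to OsrHSA and falls within 7 days.

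This count decides escalation in healthy volunteers, in a trial whose primary objective is safety. At 2 DLTs, an SRC working from 4.2.2 could escalate on blinded data. An SRC working from 4.2.4 must hold, unblind and reassess first. If both events were on OsrHSA, that is 2/6 = 33% of the treated subjects in the cohort. Only 4.2.4 makes the hold and the unblinding mandatory; the power to unblind in 5.8 is optional.

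**Working it through.** **Cohort structure.** Table 2 gives 5 cohorts of 8, split 6 OsrHSA to 2 placebo. 5 × 8 = 40, which reproduces the total in section 11.2 (30 OsrHSA, 10 placebo). Section 11.2 bases the size on clinical grounds, and no target toxicity rate is given.

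**Step 1: do the two rules count the same events?** The third criterion of 4.2.4 uses the FDA scale with the same Grade 3 cut-off as 4.2.1, with no relatedness condition and no 7-day limit. Every subject with a DLT therefore counts towards it. The reverse does not hold, since an unrelated Grade 3 event counts in 4.2.4 but is not a DLT.

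**Step 2: compare the rules at each DLT count, with nothing else happening.**

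| Subjects with a DLT | 4.2.2 | 4.2.4 | Agree? |
|---|---|---|---|
| 0 or 1 | escalate | not triggered by the DLTs | yes |
| exactly 2 | escalate | hold, unblind, reassess | no |
| 3 or more | go condition not met | hold, unblind, reassess | yes |

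The conflict lies in one row and needs no assumed rate. Because 4.2.3 makes a DLT a subject stopping event, 2 DLTs can also meet the first criterion of 4.2.4, subject to the Investigator's judgement.

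**Step 3: how often would a cohort land on that row?** The documents give no DLT rate, so p = 5%, 10% and 20% are assumed. Two cases bracket who can have a DLT:

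- only the 6 OsrHSA subjects;
- all 8 subjects at the same rate. This case is possible because the first review is blinded and section 10.2 lets timing alone make an event related, so a saline subject could be counted.

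P(exactly 2 of 6) = 15 × p² × (1−p)⁴

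- p = 0.05: 15 × 0.0025 × 0.8145 = 0.031
- p = 0.10: 15 × 0.01 × 0.6561 = 0.098
- p = 0.20: 15 × 0.04 × 0.4096 = 0.246

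P(exactly 2 of 8) = 28 × p² × (1−p)⁶

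- p = 0.05: 28 × 0.0025 × 0.7351 = 0.051
- p = 0.10: 28 × 0.01 × 0.5314 = 0.149
- p = 0.20: 28 × 0.04 × 0.2621 = 0.294

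**Step 4: effect of moving the 4.2.2 threshold.** Probability of escalating without a hold, on DLT count alone:

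| At risk | p | at most 2 DLTs | at most 1 DLT | difference |
|---|---|---|---|---|
| 6 | 0.05 | 0.998 | 0.967 | 0.031 |
| 6 | 0.10 | 0.984 | 0.886 | 0.098 |
| 6 | 0.20 | 0.901 | 0.655 | 0.246 |
| 8 | 0.05 | 0.994 | 0.943 | 0.051 |
| 8 | 0.10 | 0.962 | 0.813 | 0.149 |
| 8 | 0.20 | 0.797 | 0.503 | 0.294 |

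The difference is the probability of exactly 2 from step 3. With a threshold of fewer than 2, the two sections agree on DLT counts.

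**The case against.** The strongest reply is that the protocol already resolves this. A go criterion followed by a separately headed stop criterion is normally read with the stop as a veto. Section 4.2.4 is worded as a block with a defined next step, and 4.2 makes uninterrupted escalation depend on no stopping criterion being met. The same SRC applies both sections at a meeting held before every escalation, and section 10.9 requires it to decide whether to proceed.

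Most of this stands. A reader might infer that the documents give no indication of which section prevails. They do: 4.2 and 4.2.4 both point to 4.2.4 governing. A reader might also infer that a cohort could escalate unreviewed. It could not, because the SRC reviews every cohort and the Sponsor or Investigator can stop at any time.

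The reply does not remove the defect. Section 4.2.2 is not made subject to 4.2.4. If 4.2.4 always governs, the figure of 2 in 4.2.2 never permits escalation at the blinded review, which suggests a threshold error. Nor does 4.2.2 read as a rule for use after unblinding, since it counts out of 8 and not out of the 6 on OsrHSA. Section 4.2 is not a clean tie-breaker either: read literally, it can mean that a single DLT interrupts escalation, which is a third version of the rule.

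Three further inferences go too far:

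- **Conflict at 0 or 1 DLT when another 4.2.4 criterion is met, such as an SAE.** That is the ordinary structure of a go criterion with independent stop criteria.
- **A gap at 3 or more DLTs.** A rule to escalate at no more than 2 plainly withholds escalation at 3.
- **Dividing the chance of exactly 2 DLTs by the chance of 2 or more and calling the result a share of holds.** Section 4.2.4 counts Grade 3 or higher toxicity whether or not it is related, and has other triggers, so DLT counts are the wrong denominator.

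**Conclusion.** The point holds for one count, and there the text is wrong as written: at exactly 2 DLTs of 8, section 4.2.2 escalates and section 4.2.4 holds. What is at stake is a skipped hold and unblinding.

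The conflict follows from the definitions and rests on no assumption. Its frequency is illustrative: about 3%, 10% and 25% of cohorts with 6 at risk, or 5%, 15% and 29% with 8 at risk, at assumed DLT rates of 5%, 10% and 20%. These figures assume independent subjects, a common rate and complete cohorts. Section 4.2.2 also allows review with 6 or 7 subjects, which is not modelled. The 8-at-risk case further assumes that saline subjects have events judged related as often as OsrHSA subjects do, so it is an upper case. A reader might take the figures as chances that escalation finally fails. They are not, because 4.2.4 lets the SRC release the hold after unblinding.

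**What to change.** In 4.2.2, replace the condition with: *if fewer than 2 of 8 subjects experience a DLT and no criterion in section 4.2.4 is met, the dose will be escalated to the next level; otherwise the hold, unblinding and SRC reassessment in 4.2.4 apply before any escalation.*

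In the last sentence of 4.2, replace the closing condition with: *the escalation criteria in 4.2.2 are met and no stopping criterion in 4.2.4 is met.* This removes the zero-DLT reading.

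Naming both the count and 4.2.4 is partly redundant, since 2 DLTs always meet the third criterion of 4.2.4. It does, however, make the threshold in 4.2.2 correct when that section is read alone.

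The cost is wording in two sections. In operation, a cohort with 2 DLTs pauses and is unblinded to the SRC. The site Principal Investigator sits on the SRC, so that cohort's remaining visits (Day 15 to Day 30) would be assessed by an unblinded investigator. Section 4.2.4 already requires both the pause and the unblinding, so the change adds no burden beyond that section.
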